3. EGA
4. Name of obstetrician performing ECV procedure
5. Presence of inflated Fetal Pillow
6. Presence of terbutaline
7. Presence of palpable fetal head
8. Estimated fetal weight (kg)
9. Fetal head position *confirmed by ultrasound
10. Fetal back position
11. Position of fetal neck
12. Location of placenta
13. Amniotic fluid index (4 quadrant total)
14. Fetal station (-3 through +3)
15. Maternal cervical dilation (cm)
16. Presence of rupture of membranes within 1 hour of procedure
17. Presence of 3 or more contractions in 10 minutes immediately prior to procedure
18. Bleeding equal to a menstrual period during or within 1 hour of the ECV procedure.
19. Development of a pelvic hematoma during or within 1 hour after the ECV procedure.
20. Development of a vaginal laceration during insertion of the device, the ECV procedure, or removal of the device.
21. Presence of fetal bradycardia
22. Presence of fetal heart rate decelerations
23. Presence of delivery within 1 hour of procedure
24. VAS pain score immediately prior to ECV (-3 minutes)
25. VAS pain score immediately after insertion of Fetal Pillow (+ 2 minutes)
26. VAS pain score after inflation/sham inflation (+ 1 minute)
27. VAS pain score immediately after each ECV procedure attempt, maximum of 4 attempts (+ 2 minutes)
28. Total number of attempts
29. Procedure successful Y N (Primary Outcome) *confirmed by ultrasound
30. Fetal head position post ECV *confirmed by ultrasound
31. Number of forward rolls
32. Number of reverse rolls
33. Note which procedure was successful

34. Did patient request to have spinal or epidural anesthesia after initiation of ECV procedure (off of study protocol): Y N
35. Presence of regional anesthesia prior to ECV procedure (Excluded from study)
36. Length of time from start of procedure to hospital discharge
37. Cost of hospital stay for ECV procedure

Study Design

Research Design

This is a prospective, randomized double-blind clinical trial evaluating the effect of a balloon device to elevate the fetal buttocks during external cephalic version procedures. Eligible study population: pregnant women between 37-40 weeks estimated gestational age with a breech presenting baby and no contraindications to ECV.

Study Agent, Device, and/or Intervention Description:

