Visit 1 (ECV Procedure): The PI/Sub-I will meet the patient at the labor and delivery area, and review both the ECV procedure and possible study inclusion. The patient and researcher will sign consent forms if the patient qualifies for study inclusion and agrees to participate.

After weighing the patient, calculating a body mass index, performing a digital cervical exam, and performing a fetal non-stress test and obstetric ultrasound, all routine components of the ECV process, the PI/Sub-I will verify there are no exclusion criteria. Assuming that an ECV is still necessary and safe, the patient will receive a 0.25mg subcutaneous injection of terbutaline, a medication to quiet the uterus that is commonly used for ECV procedures. The midwife/physician performing the device inflation or sham inflation will open the randomization envelope. The researchers are blinded to patient randomization. All patients will mark a line on a 100mm VAS to assess pre-procedure pain.

The researcher will show the patient the device, open the sterile container, and insert the device into the vagina per manufacturer's guidelines for all patients in the study. All patients will mark a line on a 100mm VAS to assess post-insertion pain. The study physician will then obtain the assistance of a trained midwife/physician to inflate the device or perform a sham inflation. For the physician to remain blinded, the physician will leave the room during the time of the inflation/sham inflation. This will be documented in the source documents. Midwives/Physicians performing the inflation or sham inflation will have undergone previous training. Inflating the

Fetal Pillow is similar, although less difficult, than other balloon devices commonly used on the labor and delivery unit. The assisting midwife/physician will inflate the device with 180 mL of saline for those patients randomized to inflation. This will occur under a sheet so that the patient is blinded to the randomization scheme. If the patient is randomized to no inflation, the midwife/physician will perform a sham inflation, also under a sheet. All patients will mark a line on a 100mm VAS to assess post-inflation/sham inflation pain. The assisting midwife/physician then leaves the room, and the study physician reenters the room and proceeds with the ECV procedure.

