Regardless of randomization, at this point the ECV procedure proceeds using normal routine. Once completed, all patients will mark a line on a 100mm VAS to assess post-ECV pain. The ECV will be attempted up to four times and VAS will be assessed after each attempt.

The research physician will then remove the Fetal Pillow and perform a post procedural ultrasound to verify fetal position. Regardless of randomization, the procedure is completed per the usual routine of fetal monitoring, assessing for labor or bleeding, discussing post-procedure care, then discharge home (or, less likely, admitting for either observation or delivery).

The researcher will fill out the ECV portion of the data collection form.

Visit 2 (Labor and Delivery): There are no study interventions during this visit. The file linking the subject's FIN and study numbers will be sent to the honest broker who will then extract the data for delivery outcomes for the mother and neonate along with the final cost calculations. This data will be entered into a spreadsheet by the honest broker and then sent back to the research team. The research team will send the file linking the subject's FIN and study numbers at the intervals outlined in the safety monitoring plan (first 10 randomized subjects and every 20 subjects thereafter). The investigators are unblinded to patient randomization after the ECV procedure has been completed and during data collection for delivery and neonatal outcomes.

Data collection for patients delivering outside of AdventHealth facility. Patients will sign a release of records; study coordinator will request records from delivering facility and delivery outcomes data will be imported into spreadsheet linked to FIN.

Study Duration:

Estimated date of study completion: March 31, 2023

- Projected start date: November 1, 2020.
- Projected completion of enrollment of all study subjects: November 1, 2022.
- Projected final data collection date: March 1, 2023.

Materials of Human Origin: N/A

Study Outcome Measures (Endpoints)

Primary Outcome:

Proportion of patients undergoing ECV who have a successful outcome with and without an inflated Fetal Pillow.

Secondary Outcomes:

As noted, many of these data points are normally recorded in the medical record during an ECV procedure and subsequent delivery, regardless of study participation.

Subject Information (maternal):

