Clinical trial monitoring is conducted to ensure that the rights and well-being of trial participants are protected. Reported trial data are accurate, complete and verifiable.

Clinical trial monitoring will be conducted by AdventHealth Office of Research Integrity monitoring team to ensure compliance with all applicable federal and state regulations, ICH GCP E6 (R2) standards and approved protocol. This study will be monitored using a risk-based approach. A monitoring plan will be created to ensure patient safety, data quality and integrity is ongoing throughout the life of the study. The frequency and elements of monitoring will be outlined in the monitoring plan. The monitor will ensure study is conducted, recorded and reported as required by federal regulations and IRB of record. Monitoring will be conducted on-site and/or remote. After completion of site monitoring, a report will be provided to PI and study team. The PI and study team are required to review the report and work on significant findings or discrepancies to resolution. If any findings are required to be reported to the IRB, the PI will be made aware and prompted to self-report. All serious and continuing non-compliance is shared with the Research Oversight Committee who may require appropriate actions.

Protocol Deviations

All deviations and SAEs must be reported promptly to AH ORI and regulatory team. SAEs must be reported within 24 hours of discovery. Any SAE required to be reported to the FDA and IRB will be completed with the assistance of the central regulatory team in conjunction with the principal investigator and study team.”

Data Sharing (outside of AdventHealth Orlando): N/A

Sample Size Determination

Based on prior studies of patients without regional anesthesia who had a success rate of approximately 49%, and assuming a 1:1 allocation of intervention and control subjects, with an 80% power, and a 2-sided 5% significance level, we calculated a sample of size of 69 in each group to increase the success rate from 49% to 73.5%. Assuming a 10% case dropout rate we will enroll 76 patients in each arm (152 total participants).

Statistical Analysis Plan

Primary Objective Analysis

The success of ECV procedures for the intervention group compared to the control group will be analyzed using chi-square and Fisher exact tests. A P value of <0.05 will be considered statistically significant.

Secondary Objective Analysis

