Maternal and neonatal outcomes will be analyzed using chi-square and Fisher exact tests for categorical variables, unpaired t-tests for continuous variable, and non-parametric tests for continuous variables that are not normally distributed. P values <0.05 will be considered statistically significant.

Potential Risks and Benefits

Potential Benefits

The Fetal Pillow device may improve the ECV success rate.

Potential Risks

Although unlikely based on prior device usage during 2nd stage arrest, it is possible the device may cause vaginal bleeding, increased pain during the procedure, or either no change in success or a lower success rate compared to performing the procedure without the device. Terbutaline administration may cause maternal tachycardia, irritability, chest pressure or chest pain. While loss of confidentiality is a potential risk to patients, patient information will be de-identified prior to analysis and only study personnel will have access to patient information. The United States Food and Drug Administration has determined that this study protocol is a nonsignificant risk (NSR) study (Review # Q191927, notification received December 18, 2019).

Mitigation of Risks

Patients will be asked prior to administration of terbutaline if they have contraindications, which is standard practice prior to using this medication.

Provisions to Protect the Privacy Interest of Subjects

The steps to protect the privacy of subjects have been described previously. Briefly, study documentation and patient information will be stored in a separate file on a password-protected laptop stored in a locked office. Drs. [name], [name] and research team will have access to both files.

Early Withdrawal of Subjects

Investigator Withdrawal of Subjects.

Inability to place Fetal Pillow: If the Fetal Pillow cannot be placed, for example due to pain, or the Fetal Pillow cannot be inflated, the patient will be withdrawn from the study. However, she may undergo an attempted ECV outside of the study protocol if she wishes.

Delivery at a hospital outside of the AdventHealth Orlando system: If the patient delivers outside of the AdventHealth Orlando system she will be withdrawn from the study analysis.

Subject Request for Withdrawal from Study

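### VAS pain has no baseline-adjusted analysis although every woman gives two scores before inflation or sham, and the comparison of the per-attempt scores is left undefined

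*Combined protocol and SAP*

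**What the plan says.** Under Study Visits, Visit 1, the first pain mark comes before the device is inserted: "All patients will mark a line on a 100mm VAS to assess pre-procedure pain". All women mark the scale again after insertion and a third time after inflation or sham inflation. The first two marks therefore precede the step that differs between arms. The same section takes a post-ECV score from all patients once the procedure is completed, and adds: "The ECV will be attempted up to four times and VAS will be assessed after each attempt". Procedural Outcomes, item 27, lists the repeated score as "VAS pain score immediately after each ECV procedure attempt, maximum of 4 attempts".

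Study Outcome Measures lists pain perception among the secondary outcomes, and Potential Risks names increased pain during the procedure. Secondary Objective Analysis is the only analysis rule outside the primary outcome. For maternal and neonatal outcomes it gives "unpaired t-tests for continuous variable", with non-parametric tests where the variable is not normally distributed. It names no covariate, change score, summary score or repeated-measures model, and no way to handle women without a second, third or fourth attempt.

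**The concern.** Two separate matters arise.

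The first is precision. A score taken before the arms diverge usually predicts the later score, and regression on it narrows the confidence interval. Both tests in the plan ignore it. For an outcome that bears on a named device risk, a needlessly wide interval makes it harder either to show added pain or to rule it out.

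The second is definition. A score after attempt 2, 3 or 4 exists only for women who had that attempt, and having a further attempt depends on whether the version has already succeeded, which is the primary outcome. If the analyst applies the general rule to each score in item 27, the later tests compare subsets formed after randomization. Randomization no longer protects those comparisons, and the plan contains nothing that would steer the analyst away from them.

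**Working it through.** **The plan's own figure.** Inputs from Sample Size Determination: success 49% and 73.5%, "assuming a 1:1 allocation of intervention and control subjects", "with an 80% power, and a 2-sided 5% significance level".

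- Without continuity correction: n = [1.960·√(2·0.6125·0.3875) + 0.842·√(0.49·0.51 + 0.735·0.265)]² / 0.245² = 60.9, so 61 per arm.
- With continuity correction: (60.9/4)·[1 + √(1 + 4/(60.9·0.245))]² = 68.8, so 69 per arm, as stated.

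The documents give no figure for VAS, so 69 per arm is carried forward.

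**Precision.** The VAS SD and its correlation r with the earlier scores are not in the documents. I assume SD 25 mm and r from 0.1 to 0.6, where r is the multiple correlation if both earlier scores are used.

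- Unadjusted SE = 25·√(2/69) = 4.26 mm; half-width = 1.96·4.26 = 8.3 mm (0.334 SD, for any other SD).
- Adjusted half-width = 8.3·√(1 − r²): 8.0 mm at r = 0.3 and 6.7 mm at r = 0.6 (0.318 and 0.267 SD).
- Equivalent gain in patients = 1/(1 − r²) − 1: 10% at r = 0.3, 56% at r = 0.6, but only 1% at r = 0.1.

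**Who contributes after each attempt.** Assume attempts end on success and women leave for no other reason. Starting from 69 per arm, at the plan's 49% (control) and 73.5% (inflated):

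- Constant chance per attempt: number at attempt k = 69·(1 − p)^((k−1)/4).
- Other patterns: number at attempt k = 69·(1 − p·share of successes before attempt k). Front-loaded shares are 50%, 25%, 15%, 10%; equal shares are 25% each.

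| Pattern | Arm | Attempt 1 | 2 | 3 | 4 |
|---|---|---|---|---|---|
| Constant | Control | 69 | 58.3 | 49.3 | 41.6 |
| Constant | Inflated | 69 | 49.5 | 35.5 | 25.5 |
| Front-loaded | Control | 69 | 52.1 | 43.6 | 38.6 |
| Front-loaded | Inflated | 69 | 43.6 | 31.0 | 23.4 |
| Equal | Control | 69 | 60.5 | 52.1 | 43.6 |
| Equal | Inflated | 69 | 56.3 | 43.6 | 31.0 |

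At attempt 4 about 39 to 44 control and 23 to 31 inflated women remain.

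**Possible size of the selection effect (illustration only).** Give each woman a normal latent difficulty that lowers her chance of success at each attempt (log-odds slope 0.5 to 1.5 per SD). Calibrate to the two success rates over four attempts, and let inflation have no effect on pain. If pain correlates 0.3 to 0.7 with difficulty, the inflated arm looks more painful by 0.02 to 0.14 SD at attempt 2 and by 0.05 to 0.24 SD at attempt 4. With SD 25 mm the attempt-4 shift is about 1.3 to 6.0 mm. With zero correlation it vanishes.

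**The case against.** The strongest reply is that this is a gap in the plan rather than a faulty test, and that is largely right. A reader might infer that VAS will be tested attempt by attempt with t-tests. The documents do not say so. Item 27 sits in a data-collection list, the pain perception paragraph does not mention per-attempt scores, and the analysis rule speaks of maternal and neonatal outcomes while VAS is listed as procedural. The rule also allows a non-parametric test, which may suit a bounded scale better; that test is likewise unadjusted and equally open to selection. The post-inflation score, the score after attempt 1 and the post-ECV score from all patients do not depend on an earlier attempt having failed.

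It is also fair to say that an unadjusted comparison of randomized arms is valid. Chance imbalance in the earlier scores is not a second harm: at r = 0.3 to 0.6 a one-SE imbalance moves the estimate by r·4.26 = 1.3 to 2.6 mm, and this is already inside the 8.3 mm half-width.

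A reader might further infer that the device will look more painful the better it works. That holds only if harder versions hurt more and success is the only way out. Women may also leave by withdrawing or by asking for anesthesia (Early Withdrawal of Subjects; Procedural Outcomes, item 34). If inflation hurts more, such exits could push the other way. The illustrated shift is also small against its error: with slope 1, correlation 0.2 to 0.6 and 40.5 against 23.6 women, it is 1.4 to 4.2 mm, while the SE is 25·√(1/40.5 + 1/23.6) = 6.5 mm.

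What stands: no planned analysis uses the earlier scores, no pain contrast is defined, and separate tests after attempts 2 to 4 would not be randomized comparisons.

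**Conclusion.** The point holds as a loss of precision together with an undefined comparison. It does not show that the planned analysis is biased. The precision loss is real but moderate: it rests on an assumed SD of 25 mm and correlation of 0.3 to 0.6, and is negligible near 0.1. That the scores after attempts 2 to 4 come from post-randomization subsets follows from how they arise; the counts assume that attempts end on success. Item 33, which records the successful procedure, implies this, but no passage states it. The direction and size of any bias cannot be settled from the documents. Nor do the documents rank pain as the main tolerability outcome; it is one secondary outcome among many, without a power claim. If the analysis rule is read as not covering VAS, pain has no planned analysis at all, which makes the same change more necessary.

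**What to change.** Add a short paragraph to Secondary Objective Analysis:

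1. State that VAS pain is covered, and name two endpoints: VAS after inflation or sham, and one post-ECV VAS per woman. For the latter use the score that Visit 1 already takes from all patients on completion. The Procedural Outcomes list has no separate entry for it, so say whether it is the same mark as the score after the last attempt.
2. Compare arms on each endpoint by linear regression on arm, adjusted for pre-procedure and post-insertion VAS. Both are suitable covariates: they are marked after the envelope is opened, but before inflation or sham and by blinded women.
3. Report the separate scores after attempts 2, 3 and 4 descriptively by arm, with the number of women contributing, and without tests.

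The cost is a few lines of text; no new data or visits are needed. The small downside is that the post-ECV score includes any effect of arm on the number of attempts. That should be stated when the result is interpreted.

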The Safe Obstetric Systems Inc. Fetal Pillow is a sterile balloon device that comes in a sterile, single-use package (please see attached information). The Food and Drug Administration (FDA) has reviewed this device and determined it to be Non-Significant risk (NSR) because it does not meet the definition of a significant risk (SR) device under 21 CFR 812.3(m) of the investigational device exemptions (IDE) regulation (21 CFR 812). The device will be provided at no charge to AdventHealth Orlando. Drs. [name] or [name] will place the pillow into the vagina then the pillow will either be inflated/sham inflated by the midwife/physician with sterile saline in order to raise the fetal presenting part. After the procedure the device is deflated, removed and discarded. The Fetal Pillow device will be stored in a climate-controlled, locked storage area in the women's hospital accessible to the study investigators, midwife/physician and research personnel. It is possible that the manufacturer of this device may report de-identified study data to the FDA at a later date.

Study Site/Location and Number of Subjects

- AdventHealth Orlando.
- Estimated number of subjects: 138

Multi-Site Research Logistics/Communication Plan: N/A

Research Conducted in a Foreign Country: N/A

Community-Based Participatory Research: N/A

Subject Selection

Vulnerable Populations:

While the study population consists solely of pregnant women (some of whom may be AdventHealth Orlando employees), this research is unlikely to present more than minimal risk to subjects. This device has been used successfully to elevate the fetal head during difficult cesarean deliveries, and is FDA approved for this indication. If the device functions similarly to elevate the fetal buttocks, it may improve the success rate for the external cephalic version procedure, thus decreasing the risk that pregnant women may need a cesarean delivery. Because this research involves a procedure unique to pregnancy, it requires consent from pregnant patients. Patients unable to understand the consent process are excluded.

Inclusion Criteria

1. Breech presenting part as diagnosed by bedside sonography.
2. Pregnancy is between 37-40 weeks gestational age.
3. Live fetus.
4. Patient is \geq age 18.
5. Patient speaks English or Spanish as primary language.
6. Patient able to understand verbal and written consent

Exclusion Criteria

1. Non-breech presentation (cephalic, transverse, oblique).
2. More than 1 fetus.

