Researchers will record the cost of stay for both mothers and babies, for both the ECV procedure and the admission for delivery. This will be obtained from the mother's and child's medical record.

Data Management and Quality Plan

Data De-identification

Data will be de-identified prior to analysis. Each patient will be assigned a 4-digit code that will not contain any unique identifiers. The code will be linked to the patient's FIN which will be stored in a separate file on a password-protected laptop stored in a locked office. The de-identified data will be stored in a similar fashion in a separate file. Drs. [name], [name], the research department personnel and the honest broker will have access to both files. We anticipate that once data is entered for each individual patient, the link will be used only for the purposes of random audits to ensure data accuracy. Once data has been analyzed and results have been published, the link to the de-identified data will be destroyed after 7 years. As the assigned study number will not be linked to any PHI, we do not foresee any possible breach occurring.

Data Confidentiality, Storage, and Retention

Study documentation and paperwork will be stored behind 2 locked doors in the Center for Pediatric & Women's Research Department during the active study period. Upon study closure the paper records will remain in the research office for storage. The data file will be stored electronically on a password protected secure server at AdventHealth accessible only to study team members as listed on the personnel log. Study documentation will be retained for 7 years after study completion. After that period, paper records will be placed in hospital approved shred bins.

Electronic records will be placed in a computer electronic trash bin followed by immediate emptying of the electronic trash bin.

Data Quality

Quality control procedures for this study include source data verification by randomly selecting 10% of subjects (9 if enrollment goal is met) and verifying all values. If more than one discrepancy is found, an additional 10% of subjects will be checked. Based on those findings, additional subjects or all subjects may be verified. The AdventHealth Office of Research Integrity will create a monitoring plan and conduct internal monitoring of the study for patient safety and data integrity.

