A serious adverse event is defined as an adverse event “if, in the view of the investigator, it results in any of the following outcomes: Death, a life-threatening adverse event, inpatient hospitalization or prolongation of existing hospitalization* a persistent or significant incapacity or substantial disruption of the ability to conduct normal life functions, or a congenital anomaly/birth defect. Important medical events that may not result in death, be life-threatening, or require hospitalization may be considered serious when, based upon appropriate medical judgment, they may jeopardize the patient or subject and may require medical or surgical intervention to prevent one of the outcomes listed in this definition.

*Planned hospitalization for a pre-existing condition, or a procedure required by the clinician that is not related to the device, will not be considered a Serious Adverse Event.

Only SAEs deemed related to the device will be reported electronically to the FDA and AHIRB no later than within 10 working days after the investigator first learns of the event (21 CFR 812.150(a)(1)).

Safety Monitoring Plan

Safety Monitoring

While we consider the project to be relatively low risk, there is always the possibility of adverse events. The safety monitoring plan will include: (1) review of interim analyses of outcome data; (2) review of reports of related studies to determine whether the monitored study needs to be changed or terminated; (3) review of major proposed modifications to the study prior to their implementation; and (4) provide the study leadership with written recommendations concerning the trial including continuing, changing or terminating the study. Safety monitoring will occur after the first 10 randomized subjects and every 20 subjects thereafter. [name] M.D., Chair of Fetal Medicine Department and [name] R.N., Nurse Manager Labor and Delivery Unit will conduct the safety monitoring plan.

Data and Safety Monitoring Board (DSMB) or Equivalent: N/A

Ethical Considerations

N/A

Sharing of Results with Subjects

Patients will be immediately aware if the ECV procedure was successful. Upon completion of study data analyses, subjects will have the option to contact study team to obtain their randomization arm information.

Funding Source

There is no external funding for this research. The manufacturer of the Fetal Pillow has agreed to supply devices and have not been involved in the study design.

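### The protocol gives two enrolment totals, 138 and 152, and its audit count of 9 is 10% of neither; 138 is the total before the dropout allowance

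*Combined protocol and SAP*

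**What the plan says.** Three places in the combined protocol and SAP bear on how many women will be enrolled.

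- **Study Site/Location and Number of Subjects:** "Estimated number of subjects: 138".
- **Sample Size Determination:** "we calculated a sample of size of 69 in each group to increase the success rate from 49% to 73.5" percent, with 80% power and a two-sided 5% level. It continues: "Assuming a 10% case dropout rate we will enroll 76 patients in each arm (152 total participants").
- **Data Quality:** source data verification will be done by "randomly selecting 10% of subjects (9 if enrollment goal is met").

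No section labels 138 as an evaluable count or reconciles the three figures.

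Two other places depend on the total. Under Early Withdrawal of Subjects, women in whom the device cannot be placed or inflated are withdrawn from the study, and "If the patient delivers outside of the AdventHealth Orlando system she will be withdrawn from the study analysis". Under Safety Monitoring, "Safety monitoring will occur after the first 10 randomized subjects and every 20 subjects thereafter".

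**The concern.** The section whose job is to state the number of subjects gives a figure 14 below the number that the sample size section says will be enrolled. A reader who takes the site section as the target would close recruitment with no allowance for dropout. If losses then occurred at the assumed rate, the analysed sample would fall short of the 69 per arm on which the power statement rests.

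The audit count fits neither total. Staff who followed the printed 9 would verify fewer records than the 10% rule requires.

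**Working it through.** **1. Reproduce the planned 69 per arm.** Inputs from Sample Size Determination: control success 0.49, intervention success 0.735, 1:1 allocation, two-sided alpha 0.05, power 0.80. The difference is 0.245 and the mean proportion is 0.6125.

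Without continuity correction:

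n0 = [1.960 x sqrt(2 x 0.6125 x 0.3875) + 0.842 x sqrt(0.49 x 0.51 + 0.735 x 0.265)]^2 / 0.245^2 = 60.9

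With continuity correction:

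n = (n0 / 4) x [1 + sqrt(1 + 4 / (n0 x 0.245))]^2 = 68.8, which rounds up to 69.

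This matches the plan exactly. The total before dropout is 2 x 69 = 138, the figure in the site section.

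**2. Reproduce 76 per arm.** 69 x 1.10 = 75.9, so 76 per arm and 152 in total. Dividing by the retained fraction would give 69 / 0.9 = 76.7, so 77 per arm and 154 in total. By the same reasoning 152 x 0.9 = 136.8, just under 138. That difference is trivial.

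**3. Compare the totals.** 152 - 138 = 14 women, or 9.2% of 152.

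**4. Audit count.** 0.10 x 152 = 15.2 and 0.10 x 138 = 13.8. A count of 9 corresponds to about 9 / 0.10 = 90 subjects, a total that the document does not state anywhere. Against 152, nine records are 9 / 152 = 5.9%.

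**5. Analysed sample if 10% are lost.** 152 x 0.9 / 2 = 68.4, taken as 68 per arm. 138 x 0.9 / 2 = 62.1, taken as 62 per arm.

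**6. Exact power.** For each sample size, every possible 2x2 table was enumerated at 0.49 versus 0.735, and the probabilities of those with P < 0.05 were added. Three tests are shown because the plan names both chi-square and Fisher tests and does not say whether the chi-square is continuity-corrected.

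| Scenario | Per arm | Fisher | Corrected chi-square | Uncorrected chi-square |
|---|---|---|---|---|
| 138 enrolled, 10% lost | 62 | 76.2% | 76.2% | 81.6% |
| 152 enrolled, 10% lost | 68 | 79.8% | 79.1% | 84.2% |
| 138 enrolled, none lost | 69 | 79.9% | 79.9% | 84.4% |
| Difference, 68 vs 62 | | 3.6 points | 2.9 points | 2.6 points |

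Under Fisher and the corrected chi-square both totals fall below 80% after 10% loss. Under the uncorrected chi-square both stay above it. The 80% line therefore does not separate the two totals under any of the three tests.

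**7. Safety reviews.** On the stated schedule, reviews fall at subjects 10, 30, 50, 70, 90, 110 and 130, which is seven by 138. An eighth, at subject 150, takes place only if enrolment goes to 152.

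**The case against.** The sample size section states the enrolment rule outright, whereas the site section offers only an estimate. An estimate is not a stopping rule for recruitment, and 138 can be read as the number expected to be evaluable. That reading is possible, but the document does not give it, and it would still leave the audit count wrong.

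The power loss requires both that recruitment stops at 138 and that a full 10% is lost from the primary analysis. The primary outcome is confirmed by ultrasound straight after the procedure, so loss may be small. Out-of-system delivery is also an uncertain route to loss. The Visit 2 text provides for a records release and retrieval of delivery data for those women, which conflicts with the rule withdrawing them from analysis. No frequency is given for failure to place or inflate the device. All of this stands: the power loss is conditional and modest.

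The safety schedule counts randomized subjects, so it adjusts to actual enrolment. Seven versus eight reviews is a consequence of the total and not a fault in the monitoring plan. Likewise the operative audit rule is 10%, the 9 is an illustration, and verification expands if more than one discrepancy is found. These points limit the harm, but they do not reconcile the figures.

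The documents also do not show which total was approved by the IRB. If it was 138, moving to 152 would add 14 women to the approved number. That should be confirmed when the correction is made.

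**Conclusion.** The inconsistency is real, and it should be corrected. The two stated totals differ by 14 women, and the audit example is 6 to 7 records short of 10% of 152 (5 short of 10% of 138, rounded to 14). The sample size calculation is sound; only the carrying forward of its result failed.

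The statistical cost is 2.6 to 3.6 points of power, and only if 138 is used as the enrolment target and 10% are then lost. It is nil against the plan if no one is lost. These figures assume the plan's own success rates of 49% and 73.5%, its two-sided 5% level, and losses split equally between arms. Treating 152 as the governing total rests on its being the only figure stated explicitly as the number to enrol.

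**What to change.** - **Study Site/Location and Number of Subjects:** replace 138 with 152 enrolled, noting that 138 is the total before the 10% dropout allowance. Confirm that 152 agrees with the approved enrolment number.
- **Data Quality:** change the audit example from 9 to 15-16 subjects, which is 10% of 152.

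The 76 per arm need not change to 77.

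The cost is a wording correction in two places. It adds no patients beyond the 152 in the sample size section. The 6 to 7 further records to verify are already required by the 10% rule.
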